Obstetrical triage visits are most often secondary to uterine contractions either at term or pretermii. It is however challenging to determine whether a patient is in active labor and in need of admissioniii. The predictive value of current objective and non-objective methodologies of term or preterm deliveries remain poor. The ability to determine true labor from contractions that do not lead to cervical change becomes important in a busy triage, such as those at Montefiore, and is especially important in preterm gestations when interventions such as betamethasone injections, magnesium sulfate for

Version 5.13; June 19, 2020

neuroprotection and tocolysis can lead to decrease fetal morbidity. Women who are not in labor are at risk of medical interventions (e.g. oxytocin and cesarean birth) that can lead to increased risk of morbidity and mortality for mothers and babiesiv, v, vi, vii.

The EUM300 (electrical uterine myography)(OB Tools, Israel) is an FDA approved monitor intended for the evaluation of electrical signals originating in the uterus, thus providing a tool for measuring uterine activity as well as fetal heart rate. It is an external, non-invasive device that uses electrodes placed on the abdomen. The electrical traces can be displayed on screen in real time and data are stored and can be retrieved for later analysis.

The EUM300 was tested and found to be reliable as a non-invasive method for evaluating contractions. It is safe and effective in monitoring uterine contractionsError! Bookmark not defined.,viii. It is able to quantify uterine electrical activity and therefore to measure the strength of uterine contractions noninvasively. Thus, it has the potential to differentiate productive v. nonproductive contractions (as determined by cervical change). Although, there are yet no published studies using the EUM to assess fetal heart rate, fetal heart rate has also been accurately acquired using maternal abdominal sensors associated with this deviceix.

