#### Objectives:

Version 5.13; June 19, 2020

1. Compare the contraction tracings obtained using the EUM device vs. those obtained using the intrauterine pressure catheter vs. those obtained from external tocodynamometer among current obese patients (BMI greater than 30 kg/m^2) and nonobese patients using simultaneously obtained, 30 minute tracings with regards to the frequency of contractions, the duration of contractions, maximum height of the contractions, the total Montevideo units recorded, the timing of the contractions, and the amount of discontinuous tracings from the devices. Of the variables mentioned, the Montevideo units will only be comparable between the IUPC tracings and the EUM device.
2. Compare the fetal heart rate tracing obtained via the EUM device vs. external fetal Doppler vs. fetal scalp electrode (simultaneously obtained, 30 minute tracings will be compared) among obese patients and nonobese patients with regards to the amount of discontinuous/uninterpretable tracing, average fetal heart rate, baseline heart rate, the number accelerations, the number of decelerations, the timing of the accelerations, the timing of decelerations, the maximum fetal heart rate achieved during acceleration, the lowest fetal heart rate achieved during deceleration, and compare the degree of variability in the tracing.
3. Compare tracings of productive vs. non-productive contractions in patients presenting to triage to rule out labor (30 minutes of simultaneously obtained tracings of external tocodynamometer and EUM device will be compared) with regards to the frequency of contractions, the duration of contractions, maximum height of contractions, the timing of the contractions and the amount of discontinuous tracings from both devices, as well as changes in cervical exam on the basis of body mass index. Productive contractions are those that cause a change in cervical exam of 1 cm or more, any change in station or change in effacement of 50% or more.

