## Materials and Methods:

This will be a prospective observational study of women presenting for care to Montefiore Medical Center. Patient enrollment will occur during their obstetric triage encounter or on admission to labor and delivery. Patients will be approached if they meet the enrollment criteria. Once informed consent is obtained and the standard methods of fetal and labor assessment are in place the electrodes of the EUM will be attached to the abdominal skin surface. The electrodes will remain in place until delivery or discharge from the hospital if the patient is found not to be in labor and is discharged undelivered.

Patients will be monitored simultaneously with the EUM device and currently used methods (external or internal devices) as clinically indicated by the standard of care. Providers will be blinded to the results of the EUM device and will continue care as per current guidelines using the information obtained from the current monitoring methods. Data from the EUM devices will be captured on a study laptop computer as will data generated by the currently used fetal/uterine monitor to allow for comparison of the two systems. Each patient will serve as her own control for comparison as the data obtained from the two monitoring systems simultaneously will be compared. Patients will be monitored for 30 minutes once they consent in the labor and delivery triage rooms or labor and delivery rooms. Patients will also be asked to complete a device experience and satisfaction survey comparing the methods of monitoring. Assuming the number of minutes of unreadable tracing for the EUM is less than the Doppler by 1 minute, the standard deviation of difference in minutes by the two devices is 3 minutes, and there are 2 obstetrician readings per subject, to reach a power of 80% with 0.05 significance level, 39 patients will be needed for our primary outcome as listed below. It is anticipated that within 6-12 months, this number can be reached with recruiting efforts at both Weiler and North campus. To maximize recruitment, the co-investigator will be present daily on L&D and triage to recruit patients.

Maternal demographics to be obtained will include maternal age, ethnicity, BMI, gestational age, current medications, mode of delivery, birth weight, Apgar scores,

Version 5.13; June 19, 2020

newborn outcome, medical history and any antenatal complications, past surgical history, and postpartum course.

Primary Outcomes:

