- Continuity in readings of fetal heart rate (as measured in the number of minutes without a readable tracing in a 30 minute sample tracing) between EUM and fetal scalp electrode and external fetal heart rate monitoring from the same patient
- Continuity in readings of contractions (as measured in the number of minutes without a readable tracing in a 30 minute sample tracing) between EUM, IUPC and external tocodynamometer from the same patient

Secondary Outcomes:

- Compare average frequency of contractions between the monitoring systems
- Compare duration of contraction between the monitoring systems
- Compare maximum height of the contraction between the monitoring systems
- Compare total Montevideo units obtained between the monitoring systems
- Compare the timing of the contraction between the monitoring systems
- Compare average fetal heart rate between the monitoring systems
- Compare baseline heart rate between the monitoring systems
- Compare the number accelerations between the monitoring systems
- Compare the number of decelerations between the monitoring systems
- Compare the timing of the accelerations between the monitoring systems
- Compare the timing of decelerations between the monitoring systems
- Compare the maximum fetal heart rate achieved during acceleration between the monitoring systems
- Compare the lowest fetal heart rate achieved during deceleration between the monitoring systems
- Compare the degree of variability in the tracing between the monitoring systems. Degree of variability will be defined as the correlation between the tracings. The tracings will be broken down into 4 minute intervals and defined as minimal, moderate or marked variability and compared with each other for accuracy and

Version 5.13; June 19, 2020

consistency. Most accurate will be the internal monitor in each case, i.e. fetal scalp electrode.

- Compare patient satisfaction between the monitoring systems

Inclusion criteria:

- 1) Maternal age >18 years old
- 2) Singleton pregnancy
- 3) Gestational age of 24 completed weeks or greater based on the estimated due date as calculated from last menstrual period or early ultrasound
- 4) Category I (reassuring) fetal heart rate tracing at time of enrollment

Exclusion criteria:

- 1) Fetal anomaly or chromosome defect
- 2) Allergy to silver
- 3) Woman with implanted electronic device of any kind
- 4) Irritated skin or open wound on the abdominal wall

Recruitment Mechanisms:

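### Objective 3 compares productive with non-productive contractions between women from 24 weeks onward, and no planned analysis uses gestational age

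*Combined protocol and SAP*

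**What the plan says.** Objectives, item 3, plans to "Compare tracings of productive vs. non-productive contractions in patients presenting to triage to rule out labor", using 30 minutes of simultaneous EUM and tocodynamometer tracing. Status is defined by examination: "Productive contractions are those that cause a change in cervical exam of 1 cm or more", or any change in station, or a change in effacement of at least 50%. The item then adds "as well as changes in cervical exam on the basis of body mass index". BMI is the only patient factor it names.

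The inclusion criteria under Materials and Methods admit "Gestational age of 24 completed weeks or greater" with no upper limit. The Introduction says that contractions bring women to triage both at term and preterm. Gestational age is recorded: "Maternal demographics to be obtained will include maternal age, ethnicity, BMI, gestational age, current medications".

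The own-control statement in Materials and Methods reads "Each patient will serve as her own control for comparison as the data obtained from the two monitoring systems simultaneously will be compared". The Statistics section names a McNemar test for continuity (EUM v. IUPC), a paired t-test for continuous outcomes and otherwise routine parametric and non-parametric analysis. It allots 55 subjects to the productive v. non-productive aim.

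**The concern.** The own-control argument removes differences between women when two devices record the same woman. It does nothing when productive women are set against non-productive women. If preterm women in triage go on to cervical change less often than term women, the two groups differ in gestational age. Any tracing feature that varies with gestation (frequency, height, duration) will then differ between them even if it says nothing about whether contractions are productive.

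The Introduction says the EUM may be able to tell productive from non-productive contractions, and that recognising true labor matters most in preterm gestations. A mixed-gestation difference that only separates preterm from term women would tell a clinician nothing beyond the gestational age already known, and it would mislead most in that preterm group.

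**Working it through.** **1. The plan's own figure.** The Statistics section gives an odds ratio of 3.2, 50% discordant pairs, two-sided 5% and 80% power. The paired-proportions formula is

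n = [z_α(ψ+1) + z_β√((ψ+1)² − (ψ−1)²p_d)]² / [(ψ−1)²p_d].

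With ψ = 3.2 and p_d = 0.5 this is [1.960 × 4.2 + 0.842 × √(17.64 − 2.42)]² / 2.42 = (8.232 + 3.283)² / 2.42 = 54.8, so 55. The figure reproduces, but as a paired device comparison (EUM v. IUPC). It does not size a contrast between two groups of women.

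**2. Is the contrast between women?** The protocol does not say so outright. It follows from a label set by cervical change and a single 30-minute tracing per woman: each woman falls on one side.

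**3. Does any planned analysis handle gestational age?** McNemar and the paired t-test both compare devices within a woman. No two-group test, regression, stratification or restriction is assigned to productive v. non-productive.

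**4. Possible size.** The documents give no preterm share, productive share or gestational-age effect, so every input here except the 55 women is an assumption. Let q be the preterm share, a and b the productive shares in preterm and term women, and D the term-preterm shift in the feature, in within-stratum SD. Within each stratum the feature is unrelated to productivity.

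- Productive overall: P = qa + (1−q)b
- Term share among productive women: T₁ = (1−q)b / P
- Term share among non-productive women: T₀ = (1−q)(1−b) / (1−P)
- Spurious difference: D(T₁ − T₀)

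Example with q = 0.5, a = 0.15, b = 0.60: P = 0.375, T₁ = 0.30/0.375 = 0.80, T₀ = 0.20/0.625 = 0.32. At D = 1 the spurious difference is 0.48 SD.

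False-significance rates are from 20,000 simulated studies of 55 women per cell, using an unadjusted two-sample t-test at two-sided 5%:

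| q | a | b | T₁ − T₀ | D = 0.25 | D = 0.5 | D = 1 |
|---|---|---|---|---|---|---|
| 0.5 | 0.15 | 0.60 | 0.48 | 6.9% | 12.8% | 33.3% |
| 0.5 | 0.20 | 0.50 | 0.33 | 6.2% | 8.9% | 17.5% |
| 0.3 | 0.30 | 0.50 | 0.17 | 5.5% | 6.0% | 8.8% |
| 0.1 | 0.15 | 0.60 | 0.16 | 5.2% | 5.9% | 8.9% |
| 0.1 | 0.30 | 0.50 | 0.07 | 5.0% | 5.1% | 5.5% |

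Adding a term/preterm indicator (a linear model for the feature) brought the rate to 4.7-5.2% in all fifteen cells.

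A separate set of assumptions gives the same picture: a 28/27 split, 90% of productive women at term, and shifts of 0.25 to 1 SD. The rate is 5% if the term shares are equal, 5.1-6.4% if 80% of non-productive women are at term, and 6.6-27.8% if 50% are.

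**The case against.** **Scope.** Productive status is in neither the primary nor the secondary outcome list, and the 55 subjects are labelled as EUM v. external monitor, which is a within-woman comparison. The Statistics section says the results will feed the design of more definitive studies. All of this stands and limits the weight of the point. It does not remove it, because the productive v. non-productive comparison is a stated objective with its own sample size.

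**Silence is not commitment.** A reader might infer that the plan commits to an unadjusted contrast. It does not: it assigns no between-women test at all, and routine analysis could include adjustment. The gap is that none is written.

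**BMI.** A reader might add BMI to the list of ignored factors. Objective 3 names it, and the contraction samples are split into obese and nonobese.

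**Size.** Putting 0.48 straight into a two-sample t-test with 21 v. 34 women gives about 40%. That overstates the risk, because mixing term and preterm women also widens the SD within each group; the simulation gives about 33%. Most cells in the table lie below 10%, and with balanced gestation there is no bias.

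**Prediction.** It can be argued that a predictor needs no adjustment. But gestational age is known before the tracing starts, so the useful question is what the tracing adds to it.

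**Drugs.** The Introduction mentions, for preterm gestations, magnesium sulfate for "neuroprotection and tocolysis can lead to decrease fetal morbidity", and oxytocin as a risk for women not in labor. A reader might infer that drugs given after the tracing distort the label. That is possible, since status is set by later cervical change. However, the documents do not describe such drugs as given between the tracing and a repeat exam, and they do not state the exam interval.

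**Conclusion.** The point holds, confined to the productive v. non-productive part of Objective 3. That part is a between-women contrast over a gestational range starting at 24 weeks, and a baseline value already being collected is left out of every analysis. The possible inflation of false significance runs from none to about 33% against a nominal 5%. The upper end requires half the women to be preterm, productive shares of 15% v. 60%, and a 1 SD shift in the feature. None of these figures comes from the documents, so the range shows what could happen and does not estimate what will.

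The documents do not support extending the point to the primary continuity outcomes or to any comparison of devices within a woman.

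**What to change.** Add a paragraph to the Statistics section. Analyse Objective 3 at the woman level, with productive (yes/no) as the response and one tracing feature at a time, adjusted for gestational age and BMI. Logistic regression is the natural form. Run it identically for EUM and tocodynamometer, and report it as exploratory.

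Where uterine-active drugs between the tracing and the repeat exam are recorded, report them descriptively as a limitation. Do not rely on a repeat analysis that excludes these women: it would select on a decision made after the tracing and could itself bias the contrast. The protocol also does not list drug times or exam times as data items.

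The cost is wording only, because gestational age and BMI are already collected. The downside is somewhat wider intervals. With perhaps 20 productive women (an assumption; 55 × 0.375 = 20.6 in the example above) and three terms per model, there are about 20/3 ≈ 7 productive women per term, which is thin and is why the result should be labelled exploratory.

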## Materials and Methods:

This will be a prospective observational study of women presenting for care to Montefiore Medical Center. Patient enrollment will occur during their obstetric triage encounter or on admission to labor and delivery. Patients will be approached if they meet the enrollment criteria. Once informed consent is obtained and the standard methods of fetal and labor assessment are in place the electrodes of the EUM will be attached to the abdominal skin surface. The electrodes will remain in place until delivery or discharge from the hospital if the patient is found not to be in labor and is discharged undelivered.

Patients will be monitored simultaneously with the EUM device and currently used methods (external or internal devices) as clinically indicated by the standard of care. Providers will be blinded to the results of the EUM device and will continue care as per current guidelines using the information obtained from the current monitoring methods. Data from the EUM devices will be captured on a study laptop computer as will data generated by the currently used fetal/uterine monitor to allow for comparison of the two systems. Each patient will serve as her own control for comparison as the data obtained from the two monitoring systems simultaneously will be compared. Patients will be monitored for 30 minutes once they consent in the labor and delivery triage rooms or labor and delivery rooms. Patients will also be asked to complete a device experience and satisfaction survey comparing the methods of monitoring. Assuming the number of minutes of unreadable tracing for the EUM is less than the Doppler by 1 minute, the standard deviation of difference in minutes by the two devices is 3 minutes, and there are 2 obstetrician readings per subject, to reach a power of 80% with 0.05 significance level, 39 patients will be needed for our primary outcome as listed below. It is anticipated that within 6-12 months, this number can be reached with recruiting efforts at both Weiler and North campus. To maximize recruitment, the co-investigator will be present daily on L&D and triage to recruit patients.

Maternal demographics to be obtained will include maternal age, ethnicity, BMI, gestational age, current medications, mode of delivery, birth weight, Apgar scores,

Version 5.13; June 19, 2020

newborn outcome, medical history and any antenatal complications, past surgical history, and postpartum course.

Primary Outcomes:

- Continuity in readings of fetal heart rate (as measured in the number of minutes without a readable tracing in a 30 minute sample tracing) between EUM and fetal scalp electrode and external fetal heart rate monitoring from the same patient
- Continuity in readings of contractions (as measured in the number of minutes without a readable tracing in a 30 minute sample tracing) between EUM, IUPC and external tocodynamometer from the same patient

Secondary Outcomes:

- Compare average frequency of contractions between the monitoring systems
- Compare duration of contraction between the monitoring systems
- Compare maximum height of the contraction between the monitoring systems
- Compare total Montevideo units obtained between the monitoring systems
- Compare the timing of the contraction between the monitoring systems
- Compare average fetal heart rate between the monitoring systems
- Compare baseline heart rate between the monitoring systems
- Compare the number accelerations between the monitoring systems
- Compare the number of decelerations between the monitoring systems
- Compare the timing of the accelerations between the monitoring systems
- Compare the timing of decelerations between the monitoring systems
- Compare the maximum fetal heart rate achieved during acceleration between the monitoring systems
- Compare the lowest fetal heart rate achieved during deceleration between the monitoring systems
- Compare the degree of variability in the tracing between the monitoring systems. Degree of variability will be defined as the correlation between the tracings. The tracings will be broken down into 4 minute intervals and defined as minimal, moderate or marked variability and compared with each other for accuracy and

Version 5.13; June 19, 2020

consistency. Most accurate will be the internal monitor in each case, i.e. fetal scalp electrode.

- Compare patient satisfaction between the monitoring systems

Inclusion criteria:

- 1) Maternal age >18 years old
- 2) Singleton pregnancy
- 3) Gestational age of 24 completed weeks or greater based on the estimated due date as calculated from last menstrual period or early ultrasound
- 4) Category I (reassuring) fetal heart rate tracing at time of enrollment

Exclusion criteria:

- 1) Fetal anomaly or chromosome defect
- 2) Allergy to silver
- 3) Woman with implanted electronic device of any kind
- 4) Irritated skin or open wound on the abdominal wall

Recruitment Mechanisms:

Clinicians will ask patients during their obstetric triage encounter or on admission to labor and delivery after they meet enrollment criteria whether they are interested in the study. Informed consent will then be obtained by the research clinicians.

Informed Consent:

Copies of the informed consent and a brochure detailing the device will be distributed to offices at Montefiore where prenatal care is provided to allow patients to provide provisional consent in advance of presenting to the labor and delivery unit. If at that time the patient refuses participation, it will be documented in the patient's chart and the patient will not be approached a second time. Patient's providing provisional consent will be given a second opportunity to provide consent or to refuse at the time they present

Version 5.13; June 19, 2020

to the labor and delivery unit and are eligible to initiate the protocol. If at the time they are approached for actual involvement in the protocol, they are in too much pain to have the informed consent discussion and provide consent, they will not be considered for participation.

Patient consent will occur on admission to the obstetrical triage or labor and delivery unit. Because patients presenting to our units may be in pain and pain may compromise cognition and judgment, at the time of actual enrollment, the principal investigator or his or her designee will assess the capacity of the patient to provide ethically and legally adequate informed consent and will document that finding in the research record. If the patient is capable of providing informed consent the patient will be: engaged in the discussion of the risks and benefits of the protocol, reminded of his or her prior provisional consent (if it had been obtained) and asked to consent to or to refuse participation.

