#### Purpose:

We propose to perform a study to validate the accuracy and clinical usefulness of the EUM device by comparing it with simultaneous use of current methods (both external or internal devices) among obese patients and patients with normal body mass indexes (BMI). Our goal is to show that the EUM device is a noninvasive tool of similar utility to the fetal scalp electrode and the IUPC, and superior the traditionally used noninvasive devices (Doppler ultrasound and tocodynamometer).

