#### Device Description:

The EUM300 is composed of three units: Disposable electrode, Maternal unit and Interface unit.

Disposable electrode applied part – Proprietary bio-compatible patch electrode array with nine Ag/AgCl and hydrogel connections. Electrode is made by US based manufacturers: Lead-Lok, Sandpoint, ID and Molex, Naperville, IL.

Maternal Unit – The maternal unit is connected via a proprietary connector to the electrode. The EMG signals are amplified by an analog front-end. OB-Tools Algorithm runs on a DSP board and the result – Fetal Heart Rate and Uterine Activity are transmitted via Bluetooth. The unit contains a 4.2V Li-Ion rechargeable battery. The battery allows 24h of work and must be charged away from the patient.

Interface unit – Wall mount unit translates the information received from a paired Bluetooth Maternal unit. In this setup the EUM is used as a secondary system, one that

Version 5.13; June 19, 2020

is not involved with clinical decisions. In this case a PC computer receives the bluetooth transmission from the maternal unit and saves it into an Excel readable file. A primary monitor that is used for clinical decisions may also be connected to the PC and its data is recorded into the same file for comparison. The file format is a simple 6 column format: Date, Time, EUM UA, EUM FHR, Monitor UA, Monitor FHR. The file can be read and analyzed using Excel, Matlab and other statistical tools.

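### The fetal heart rate primary outcome measures continuity only, and no agreement criterion supports the aims of accuracy, similarity to the scalp electrode or overall superiority to Doppler

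*Combined protocol and SAP*

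**What the plan says.** Under Primary Outcomes (Materials and Methods), the fetal heart rate outcome is "Continuity in readings of fetal heart rate (as measured in the number of minutes without a readable tracing" in a 30-minute sample, compared between EUM, FSE and external monitoring in the same woman. The sample size, given in Materials and Methods and again in Statistics, rests on the same quantity: "Assuming the number of minutes of unreadable tracing for the EUM is less than the Doppler by 1 minute", with "the standard deviation of difference in minutes by the two devices is 3 minutes" and "there are 2 obstetrician readings per subject". This leads to 39 patients for 80% power at the 0.05 level. No section defines what makes a minute readable. Objective 2 speaks of discontinuous or uninterpretable tracing, which is also not a test of correctness.

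The Purpose section sets out to "validate the accuracy and clinical usefulness of the EUM device". Its stated goal is to show EUM of similar utility to the FSE and the intrauterine pressure catheter, and superior to Doppler and the tocodynamometer.

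The secondary outcomes compare average and baseline rate, the number and timing of accelerations and decelerations, the peak and lowest rates in them, and variability in 4-minute intervals. The FSE is named as the most accurate device for variability only. Statistics assigns a paired t-test to continuous outcomes.

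On the device, the Introduction says "there are yet no published studies using the EUM to assess fetal heart rate". The same sentence adds that heart rate has been acquired accurately with abdominal sensors associated with the device. Device Description says "OB-Tools Algorithm runs on a DSP board" and that its result is the heart rate and uterine activity sent by Bluetooth. The comparison file has one EUM heart rate column and one monitor heart rate column.

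**The concern.** Continuity and correctness are different properties. A device that shows a plausible but wrong rate for a minute can score better on this outcome than one that correctly shows nothing. The outcome therefore cannot tell a gain in usable tracing from a gain in tracing of unknown quality.

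The difficulty is greatest where EUM would gain its advantage, in minutes that EUM can read and Doppler cannot. In a woman monitored by Doppler, the file's single monitor column offers no second trace against which to check those minutes.

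What is at stake is the conclusion. A significant difference in unreadable minutes could be reported as meeting the aims in the Purpose section, although no planned criterion tests agreement with a reference.

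**Working it through.** **Inputs.** From Materials and Methods and Statistics: difference δ = 1 minute, SD of the paired difference 3 minutes, two readings per woman, 80% power, significance level 0.05, n = 39. From the end of Statistics: paired t-test. Not given: sidedness for this outcome (two-sided assumed), the correlation ρ between the two readings (shown over a range), and any frequency of wrong-but-readable minutes (assumed below).

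**The plan's own figure.** For the mean of two readings, n = [SD × (z₀.₉₇₅ + z₀.₈₀)/δ]² × (1+ρ)/2. Here (3 × 2.802)² = 70.6.

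- ρ = 0: 70.6 × 0.50 = 35.3, so 36 (38 by noncentral t).
- ρ = 0.1: 70.6 × 0.55 = 38.9, so 39 (41 by noncentral t).
- ρ = 1, equivalent to one difference per woman: 71 (73 by noncentral t).

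The stated 39 is therefore reproduced for nearly independent readings. The arithmetic is not the issue.

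**What the test responds to.** Let w be the net excess of wrong-but-readable minutes, EUM minus Doppler, per 30 minutes. Then

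readable advantage = advantage in correct minutes + w.

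The test sees only the left side. Set the advantage in correct minutes to 0, keep the SD at 3 and use n = 39. The SD of the per-woman mean is 3√((1+ρ)/2), the noncentrality is w√39 divided by that SD, and the critical value on 38 df is 2.024.

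| ρ | SD of mean | Noncentrality, w = 0.5 | P(EUM significantly better), w = 0.5 | Noncentrality, w = 1 | P(EUM significantly better), w = 1 |
|---|---|---|---|---|---|
| 0 | 2.12 | 1.47 | 30% | 2.94 | 82% |
| 0.1 | 2.22 | 1.40 | 28% | 2.81 | 78% |
| 1 | 3.00 | 1.04 | 17% | 2.08 | 53% |

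At w = 0 the probability is 2.5% in every row. These values are the plan's power curve read at a readable advantage of w. They show what the test cannot distinguish, and say nothing about how often EUM is wrong. One minute is 1/30 = 3.3% of the sample.

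**Whether the secondary outcomes close the gap.**

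- Average rate is insensitive to brief errors. One minute wrong by an assumed 60 bpm moves a 30-minute mean by 60/30 = 2 bpm.
- A paired t-test on rate tests the mean difference, so errors in opposite directions cancel.
- Event timing, peak and lowest rates, and 4-minute variability with the FSE as reference are finer and could expose some errors. They carry no agreement limit or success criterion.
- No text makes the primary conclusion depend on any of them.

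**The case against.** Continuity is a legitimate outcome in its own right. The Purpose names clinical usefulness beside accuracy, and a trace that drops out less is useful. Providers are blinded to EUM, and Statistics says the results will help design more definitive studies. The plan contains no rule that turns a significant continuity result into a claim of accuracy. All of this stands, and it is why the continuity comparison should be kept.

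A reader might also infer several stronger things that the documents do not support.

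- *EUM shows wrong rates.* Nothing in the documents says so, and the Introduction reports accurate acquisition with associated sensors. Doppler can also be readable and wrong: the Introduction says its three-beat averaging limits its accuracy. Only the net excess matters.
- *Every wrong minute is counted as readable.* Readability is undefined, and two obstetrician readings per woman are assumed. Readers may reject implausible traces, although no rule tells them to.
- *Accuracy is ignored, or examined only through 30-minute averages.* The secondary outcomes include event timing, extremes and 4-minute variability against the FSE.
- *Nothing but the algorithm's output is kept.* The Device Description covers the comparison file. The Introduction says device data are stored and can be retrieved.
- *The 78% to 82% measures the harm.* It depends wholly on an assumed w.

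After these corrections one gap remains. The aims include accuracy and similarity to the FSE, and no analysis in the plan has a criterion for either.

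**Conclusion.** The point holds in a limited form. A positive fetal heart rate primary result would support better continuity of EUM. It would not by itself support accuracy, similarity to the FSE or overall superiority to Doppler, because readable minutes are not tested for correctness and the accuracy-related secondary outcomes have no agreement limit and no bearing on the primary conclusion.

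The possible size is conditional. With a net excess of 1 wrong EUM minute in 30 and no gain in correct minutes, a significant EUM advantage at n=39 has probability 78% to 82% (53% with one difference per woman). With 0.5 minutes it is 28% to 30% (17%). These figures assume a two-sided 0.05 paired t-test, an SD that stays at 3, and between-reader correlation of 0.1 to 0 for the ranges. The documents supply no rate of wrong minutes.

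This should be fixed as a cheap improvement. It does not invalidate the continuity comparison.

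**What to change.** Keep the continuity comparison as planned. Before any tracing is read, define a readable minute and fix a bpm agreement band. Then:

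- **Women with an FSE:** classify each EUM minute against the FSE as readable and concordant, readable and discordant, or unreadable. Analyse usable minutes (readable and concordant) alongside readable minutes.
- **Women with Doppler only:** report minutes in which both devices are readable but differ by more than the band. Tabulate minutes readable on EUM but not on Doppler separately, as unverified.
- **Conclusions:** limit the EUM v. Doppler test to a statement about continuity. Base any statement on accuracy or similarity to the FSE on the concordance results.

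The discordant share in FSE women should not be used as a condition on the minutes gained over Doppler. A share and a count of minutes are not comparable, and with one monitor heart rate column the two may come from different women.

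The cost is protocol and analysis wording plus a script on the heart rate columns already recorded. No further patients or procedures are needed. The drawbacks are that EUM may look less favourable and that verification is confined to women with an FSE.
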